1 OBJECTIVES AND ENDPOINTS

1.1 Objectives

1.1.1 Primary Objective:

Everolimus/Ribociclib cohort (DIVa)

The primary objective is to investigate the clinical efficacy of everolimus/ribociclib in combination with endocrine therapy (as assessed by the CTC clearance rate) in postmenopausal patients with hormone-receptor positive, HER2-negative metastatic breast cancer and persisting HER2-negative circulating tumor cells (CTC).

Eribulin cohort (DIVb)

The primary objective is to investigate the clinical efficacy of eribulin (as assessed by progression-free survival, PFS) in patients with HER2-negative, hormone-receptor positive metastatic breast cancer and indication to chemotherapy or triple-negative metastatic breast cancer both with persisting HER2-negative CTC.

1.1.2 Secondary Objectives:

In General

- Evaluation of efficacy of the study treatment as assessed by overall response rate (ORR), disease control rate (DCR), and overall survival (OS)
- Assessment of the dynamic of CTCs by longitudinal comparisons of CTC counts before during and after treatment and evaluation of the value of different measures of CTC dynamics for prognosis and assessing therapy efficacy
- Assessment of Quality of Life (QoL) as evaluated based on the EORTC QLQ-C30 and EORTC QLQ-BR23 questionnaires
- Assessment of quality-adjusted survival (as calculated by the Q-TWiST method)
- Assessment of toxicity, safety and tolerability of the study treatments (everolimus/ribociclib or eribulin)
- Evaluation of compliance to study procedures

Everolimus/Ribociclib cohort (DIVa)	Eribulin cohort (DIVb)

 • Evaluation of efficacy of the study treatment as assessed by progression-free survival (PFS) • Establishing of immune histochemistry and assessment of the response of phosphorylated ribosomal protein S6 (pS6) analysed in CTCs to treatment • Evaluation of the correlation of pS6 levels analysed in CTCs with clinical outcome (PFS) • Assessment of the activation of the PI3K/Akt/mTOR-pathway in CTCs (SNaPshot methodology for PI3KCA mutations) • Establishing and assessment of immune histochemistry for pAKT and PTEN in CTCs • Establishing the analysis of estrogen-receptor 1 (ESR-1) mutations via SNaPshot methodology in CTCs • Expression of Epithelial Mesenchymal Transition inducing transcription factors in CTCs • Resistance to anoikis in CTCs • Expression of LKB1 in CTC • Molecular profiling of CTCs in breast cancer • Quantification of circulating microRNAs miR-125a, miR-125b, miR-18a und miR18b in the serum of breast cancer patients 	
 • Evaluation of efficacy of the study treatment as assessed by new metastasis-free survival (nMFS) • To determine the androgen receptor (AR) expression on CTCs using AR specific monoclonal antibody • To determine mutation status of AR by PCR amplification of AR exons followed by sequencing analysis • To determine PIK3CA mutations on CTC based on SNaPshot technology • To isolate Eribulin resistant CTCs from TNBC patients and to characterize them on the molecular level with a special focus on the correlation between EMT and their capacity to overcome anoikis. • To determine the predictive values of the detection of aberrant 53BP1 signals on CTCs and genetic alterations in BRCA1 in peripheral blood samples as potential biomarkers for responsiveness to therapy with Eribulin in patients with TNBC and persisting HER2-negative CTCs. • To assess the dynamic of 53BP1 signals on CTCs by longitudinal comparisons before, during, and after treatment, to evaluate the suitability of the different measures for assessing therapy efficacy

1.2 Endpoints

1.2.1 Primary Endpoint:

Everolimus/Ribociclib cohort (DIVa)

CTC clearance rate: Proportion of patients with at least one CTC detected in 7.5 ml of peripheral blood drawn before treatment that show no evidence of CTCs in the blood after treatment (CTC prevalence as assessed using the Cell-Search® System; Veridex LLC, Raritan, USA).

Eribulin cohort (DIVb)

The primary endpoint is progression-free survival (PFS), defined as time interval from date of recruitment until progressive disease (PD) or death from any cause, whichever comes first (as defined by RECIST guideline version 1.1). If a patient has not had an event, progression-free survival is censored at the date of last adequate tumor assessment.

1.2.2 Secondary Endpoints:

In General

- Overall response rate (ORR): rate of complete (CR) and partial responses (PR) in patients in whom target lesions were defined
- Disease control rate (DCR): rate of patients who were assessed as having a PR or a CR or who had stable disease (SD) for at least 6 months
- Overall survival (OS), defined as the time interval from start of treatment until death due to any cause. If a patient is not known to have died, survival is censored at the date of last contact
- Dynamic of CTC: Descriptive statistics of regular CTC counts
- Level of compliance to the study protocol
- The assessment of safety will be based mainly on the frequency of adverse events. Other safety data (e.g. laboratory values, vital signs, and special tests) will be considered as appropriate
- Quality of life (QoL) as assessed by evaluation of the EORTC QLQ-C30 and EORTC QLQ-BR23 questionnaires
- Quality-adjusted survival (as assessed by the Q-TWiST method), with the utility scores for the different health states being prospectively determined in the clinical trial subjects based on the EORTC QOL C30 questionnaire

(CR, PR, and SD are defined according to the RECIST Version 1.1 criteria) (Eisenhauer 2009)

Everolimus/Ribociclib cohort (DIVa)	Eribulin cohort (DIVb)

 • Progression-free survival (PFS), defined as time interval from date of recruitment until progressive disease (PD) or death from any cause, whichever comes first (as defined by RECIST guideline version 1.1). • Dynamic of CTCs: changes in CTC counts from baseline numbers (start of treatment) to the time of first radiological tumor evaluation after about 12 weeks, and every 12 weeks thereafter until progression • Levels of pS6 at baseline, at first radiological tumor assessment after about 12 weeks, and at the time of progression • Change in the activation of the PI3K/Akt/mTOR-pathway in CTCs as assessed by longitudinal comparisons (at baseline, after 12 weeks, at time of progression) • Estrogen-receptor 1 (ESR-1) mutations in CTCs at baseline, after 12 weeks and at time of progression 	
 • Dynamic of CTCs: changes in CTC counts from baseline numbers (start of treatment) to first (6 weeks) and second (12 weeks) control visit as well as the time of progression or end of treatment. • New metastasis-free survival (nMFS), defined as time from recruitment to death or progression due to appearance of a new metastasis, whichever comes first. If a patient has not had an event, nMFS is censored at the date of last adequate tumor assessment.

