4.3 Schedule

The individual study participation begins with the screening visit, consists of endocrine therapy plus everolimus/ribociclib or therapy with eribulin (depending on the treatment cohort) and ends with disease progression, the patient's death or with completion of the follow-up period. The estimated maximum duration of individual study participation is 36 months and 3 weeks both for the everolimus/ribociclib cohort and the eribulin cohort.

Patient participation is divided in 3 consecutive periods:

Pre-Treatment Evaluation Period:

Content:	Examinations and collection of data relevant to decide on patients' eligibility for further study participation. Informed consent 1
Period:	From screening to inclusion
Maximum duration:	3 weeks
Visits:	From Screening Visit to end of Inclusion Visit

Treatment Period:

Content:	Endocrine therapy combined with everolimus/ribociclib or chemotherapy with eribulin.
----------	--

Assessment of efficacy and safety data.
Informed consent 2 and 3

Period: From inclusion until disease progression or occurrence of other criteria for treatment discontinuation

Maximum duration: 12 months* (both for the everolimus/ribociclib cohort and the eribulin cohort) or until progress / death or discontinuation due to toxicities or other reasons

Visits: From Inclusion Visit to Conclusion Visit (4 weeks after last application of everolimus/eribulin)

*After treatment period the treatment with everolimus/ribociclib or eribulin can be extended if medically indicated. Patients will be followed up for toxicity and efficacy in such cases. The drug will be supplied by Novartis (everolimus/ribociclib), respectively Eisai (eribulin) on study terms for the duration of the individual study participation (including 2-year-period of follow-up assessments).

Follow-Up period:

[figure not shown]
Content: Assessment of survival, adverse events and concomitant medication. Treatment of the metastatic disease at the investigator's discretion

Period: From end of study treatment until the patient has either died or completed the 24-months follow-up period

Maximum duration: 24 months (estimation)

Visits: From Conclusion Visit of the Treatment Period to the last Follow-Up Visit

Figure 9: Clinical Trial Design

Entire Study:

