8.6.2 Definition of end of the study

The study end is planned for a maximum of three years after recruitment of the last patient (LPLV). Study will be

terminated after death or complete two year follow-up off all patients. Patients will be followed for safety for 28 days after the individually last dose of everolimus/ribociclib/ eribulin study drug. At the end of the study the current progression and survival status for all patients will be updated finally and recorded in the eCRF.

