9.2 Evaluation during Follow-Up Period (after Treatment Period)

Follow-up procedures are study specific and not part of the usual routine in case of metastasizing breast cancer.

Between two and four weeks after conclusion visit of the treatment period and then at least every three months the following is assessed during routine visits in the clinical trial center or via telephone call:

- Adverse events which are \geq grade 3 NCI CTCAE and/or serious
- Concomitant medication
- Survival

Therapy during Follow-Up Period is as described in section 12.1.3 “Therapy after end of protocol treatment”.

10 **CRITERIA FOR MEASUREMENT OF STUDY ENDPOINTS**

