If on baseline tumor evaluation there are at least two measurable lesions a maximum of five in total and a maximum of two per organ are selected as target lesions. In case of lymph nodes the length of the short axis, in case of other lesions the longest diameter is recorded. Target lesions should be selected on the base of their size (lesions with the longest diameter) and be representative of all involved organs, but in addition should be those which lend themselves to reproducible repeated measurements. The sum of the lesion diameters (LD) assessed for all target lesions is calculated and reported as baseline sum LD. All other lesions are considered non-target and reported without diameter whether measurable or not.

- On the regular tumor evaluations during treatment period, which are performed every 3 months LD is reassessed. All non-target lesions are reported “present”, “absent” or “unequivocal progression”.
- Generally:
Response and progression of metastatic disease is evaluated using the international guidelines Version 1.1 proposed by the RECIST committee (Eisenhauer 2009).
For detailed instruction on lesion measurements, follow-up of non-target lesions and special considerations regarding lymph nodes, bone lesions, cystic lesions, lesions not observed at baseline and lesions with prior

radiologic treatment please refer to the **RECIST guideline Version 1.1** (Eisenhauer 2009).

Assessment of tumor response

Tumor response is assessed as follows:

- *Evaluation of target lesions:*

Complete Response (CR):	Disappearance of all target lesions. Any pathological lymph nodes (whether target or non-target) must have reduction in short axis to < 10 mm
Partial Response (PR):	At least a 30% decrease in the sum of diameters of target lesions, taking as reference the baseline sum diameters
Progressive Disease (PD):	At least a 20% increase in the sum of diameters of target lesions, taking as reference the smallest sum on study (this includes the baseline sum if that is the smallest sum on study). In addition to the relative increase of 20% the sum must also demonstrate an absolute increase of at least 5 mm. (Note: The appearance of one or more lesions is also considered progression)
Stable Disease (SD):	Neither sufficient shrinkage to qualify for PR nor sufficient increase to qualify for PD, taking as reference the smallest sum diameters while on study.

- *Evaluation of non-target lesions:*

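### PFS and nMFS count deaths from a 24-month follow-up that records no progression, so censoring depends on survival; nMFS and the late PFS curve are distorted, the eribulin median PFS hardly at all

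*Protocol*

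**What the plan says.** - **PFS (Protocol 1.2.1, DIVb primary endpoint):** "defined as time interval from date of recruitment until progressive disease (PD) or death from any cause, whichever comes first". The censoring rule is "If a patient has not had an event, progression-free survival is censored at the date of last adequate tumor assessment".
- **nMFS (1.2.2, DIVb secondary endpoint):** "defined as time from recruitment to death or progression due to appearance of a new metastasis, whichever comes first". Again, "If a patient has not had an event, nMFS is censored at the date of last adequate tumor assessment".
- **Tumour assessment (10.2.1):** "On the regular tumor evaluations during treatment period, which are performed every 3 months LD is reassessed". The Appendix II flow sheet marks RECIST evaluation at the Inclusion Visit and the Control Visits only. The Conclusion Visit list in 9.1 contains none.
- **Treatment period:** at most 12 months. Permanent discontinuation of eribulin starts the two-year follow-up (8.4.2).
- **Follow-up (9.2):** "Between two and four weeks after conclusion visit of the treatment period and then at least every three months the following is assessed", by visit or telephone. The list is grade 3 or higher or serious adverse events, concomitant medication and survival. Appendix II agrees.
- **Later progression data:** section 4.3 says of patients whose study drug is extended, "Patients will be followed up for toxicity and efficacy in such cases". Section 8.6.2 adds "At the end of the study the current progression and survival status for all patients will be updated finally and recorded in the eCRF", and 13.1.1 has a similar sentence. None of these gives a schedule or asks for dates, and none appears in the follow-up list.
- **DIVa PFS (1.2.2) and 10.1.2:** no censoring rule is stated.

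**The concern.** The event rule and the assessment schedule do not fit together. Deaths are ascertained for up to 24 months after treatment. Progressions are ascertained only while the patient is on treatment. Someone who stops for toxicity or completes 12 months without progression is kept at risk until death if she dies in follow-up. If she survives, she is removed at her last scan. Whether she is censored, and when, thus depends on her later survival, and Kaplan-Meier estimation assumes that it does not.

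nMFS is more exposed. Progression in an existing lesion is not an nMFS event, but it ends treatment and with it the scheduled scans. A later new metastasis need not be recorded, yet a later death still counts.

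PFS is the DIVb primary endpoint, and 15.2 promises the Kaplan-Meier function as well as the median. Section 2.7.3 motivates nMFS by a difference of 4.2 versus 3.1 months, which is 1.1 months. An error of similar size would matter. An analysis plan cannot repair this alone, because it cannot recover progression dates that were not collected.

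**Working it through.** **Inputs from the protocol.** Median PFS 3.7 months and n = 108 (15.3); scans every 12 weeks for at most 12 months; survival follow-up 24 months.

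**Assumptions, not in the protocol.** Exponential times; 5% of the PFS hazard is death without progression; median survival after progression 9 months (this gives a simulated median OS of about 14.2 months, against 13.1 on eribulin in the pivotal phase III trial, 2.7.3); 10% stop without progression by month 12 (range 0 to 30%); 50% of progressions are new metastases (range 30 to 70%); after progression in an existing lesion, new metastases arise at the same rate as before.

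**1. The plan's own figure.** Exponential model: 1.96/√108 = 0.1886, and 3.7 × (e^0.1886 − e^−0.1886) = 1.40 months. Scaling the cited interval (3.3 to 3.9, n = 508): 0.6 × √(508/108) = 1.30 months. Both agree with the stated 1.3 to 1.5 months.

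**2. How many patients are exposed.** Progression-free at 12 months: 2^(−12/3.7) = 0.106, and 108 × 0.106 = 11.4 patients. About 89% of PFS events therefore fall inside the scanning window, so the median should be safe and the tail should not.

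**3. Simulation, n = 108.** The protocol rule scores an event if progression occurs before leaving treatment, otherwise an event at death in follow-up, otherwise censoring at the last scan. Complete ascertainment means that every progression and new metastasis is seen. Base case:

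| Quantity | Protocol rule | Complete ascertainment |
|---|---|---|
| Median PFS, months | 3.78 | 3.76 |
| PFS at 12 months | 11.4% | 10.7% |
| PFS at 18 months | 8.1% | 3.5% |
| PFS at 24 months | 4.4% | 1.1% |
| Median nMFS, months | 7.18 | 6.25 |
| nMFS at 12 months | 30.8% | 23.6% |
| nMFS at 18 months | 17.4% | 10.1% |

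The closed form 2^(−18/3.7) = 3.4% confirms the true 18-month PFS.

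**4. Sensitivity.**
- With 0 to 30% stopping without progression, the shift in median PFS runs from 0.00 to 0.09 months, and 18-month PFS under the protocol rule from 7.5% to 8.9%.
- With 70% of progressions being new metastases, median nMFS is 5.50 versus 5.01 months and the 12-month rate 22.7% versus 16.7%. With 30%, it is 9.32 versus 8.22 months and 38.8% versus 33.0%.
- A second, separately built simulation under the same headline assumptions, with 50 to 70% new metastases, gave an nMFS median 0.6 to 1.2 months too long and a 12-month rate 8 to 10 points too high. Hence the quoted ranges of about 0.5 to 1.2 months and 6 to 10 points.

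**5. If later progression data do arrive.** If 30%, 60% or all of those still on treatment and progression-free at 12 months continue to be scanned, 18-month PFS under the rule is 6.7%, 5.5% or 4.2%. If the final update supplies progression dates for half or all patients, it is 5.5% or 3.4%.

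**The case against.** **The primary result is sound.** DIVb is sized on the precision of the median, and a shift below 0.1 months is negligible beside an interval about 1.4 months wide. This stands. A reader might infer that the primary estimate is biased; the numbers do not support that. nMFS is secondary and, under 15.2, exploratory.

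**The protocol does mention later progression data.** Sections 4.3, 8.6.2 and 13.1.1 do, and 13.1.3 lets eribulin continue until progression. This stands in part. A reader might infer that the curves must fall to zero because only patients who will die remain at risk after month 12. That holds only if those sections yield nothing. In addition, the DIVb PFS curve reaches zero in about 87 to 89% of simulated trials even with complete scanning, so a zero end point is no evidence of bias. Still, without dates or a schedule these sentences do not secure usable data, and they do not match the list in 9.2.

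**DIVa.** A reader might extend the result to DIVa and predict a grossly false curve by month 36. The protocol states no censoring rule for DIVa PFS. The long medians that such a prediction needs (16.0 and 16.0 + 9.3 = 25.3 months, 2.7.2) come from patients with no prior therapy for advanced disease, whereas DIVa requires progression after endocrine therapy. For everolimus plus exemestane, 2.7.1 reports 7.8 months.

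**Counting any death is a normal PFS definition.** Agreed. The fault lies in pairing it with a follow-up that does not record progression.

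**Conclusion.** The point holds in limited form and should be corrected. As written, censoring of PFS and nMFS depends on later survival. Under the stated assumptions the DIVb median PFS is essentially unaffected. The PFS curve after about 12 months is unreliable (18 months: about 8% versus 3.5%). nMFS is overstated even in its median, by about 0.5 to 1.2 months, and by about 6 to 10 points at 12 months.

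The error need not run in one direction throughout: missed progressions dated at death push a curve up, while removing survivors at their last scan pulls it down. DIVa PFS beyond 12 months would be unreliable in the same way if the DIVb censoring rule is applied to it. The sizes are simulation results, not trial data, and shrink to the extent that dated progression is in fact obtained after treatment.

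**What to change.** 1. Add to the existing three-monthly contact (9.2, Appendix II), from routine imaging and without extra scans: date of last tumour imaging; progression yes/no with date; new metastasis yes/no with date.
2. For nMFS, continue this after progression in existing lesions until a new metastasis or death. Without this step the nMFS error remains.
3. Require dates in the final status update (8.6.2, 13.1.1), and bring 4.3 and 9.2 into line.
4. State the same PFS censoring rule for DIVa.
5. Where no dated progression data exist after the last scheduled scan, report the PFS and nMFS curves only to that time. This protects the PFS tail but does not by itself repair nMFS within the first 12 months.

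With complete progression dates, simulated 18-month PFS returns to 3.4%, against a true 3.5%.

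Two tempting alternatives are not advised. Counting deaths only within 24 weeks of the last scan, used alone, gives 12-month PFS of 5.0% against a true 10.7%, which is worse than the present rule. Treating progression in existing lesions as a competing event changes the stated nMFS endpoint and its comparability with the results in 2.7.3.

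Cost: a few eCRF items on an existing form, slightly more site data entry, and shorter reported curves where follow-up imaging is missing.
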